Participants will be recruited from primary care offices affiliated with Eskenazi Health and IU Health.

Step 1: Identification of Potential Participants

- Participants will be identified in a variety of ways and will be tailored based on the recruitment site. Patients will be identified via the Indiana Network for Patient Care, (INPC) which can access patient lists by doctor, clinic, and PC clinic schedules. Physicians will be notified first of their patients' potential eligibility and be asked if the COADS study personnel may approach the patient and their family member for participation. Physicians are routinely given 2 weeks to review the list of their potentially eligible patients (per IU PBRN). Physicians will be given the opportunity to opt-out of study participation at this time. Following either approval from the PCPs, or at the end of the two-week review period study personnel will mail out an introductory letter, email or post card to patients. Study personnel will then approach patients via telephone, email or in person in the-clinic to confirm eligibility and obtain informed consent.
- We will consider any man or woman 65 years or older who has not been diagnosed with AD or related dementia, and is considered an active patient (PCP visit in- person or virtual within 24 months including requests for prescription refills, or questions and is able to provide consent, and speaks English.

- We will approach the primary family member/caregiver/informant for each eligible participant. Family members will be eligible if they are patient-identified or self-identified as a person who is likely to provide care for the patient, is 21 years or older, lives within a 50-mile radius of the participant, is able to consent, and speaks English
- Rolling enrollment will take place over 36 months with an average monthly recruitment of 50 dyads

Step 2: Enrollment

- Following eligibility determination and the informed consent process (including HIPAA release), dyads will be randomly assigned to one of three groups, stratified by site (e.g. Eskenazi or IUH). Dyads are officially enrolled at this point.

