will undergo active surveillance throughout the study via EHR to monitor any AD screening, new diagnoses of AD, and/or new prescriptions for anti-dementia medications. At the 24-month outcome assessment, study personnel will administer the Short Informant Questionnaire on Cognitive Decline in the Elderly (IQCODE) to the family member and the patient will complete the Cognitive Change Index (CCI).

- Rolling enrollment will take place over 36 months with an average monthly enrollment of 50 dyads. The proposed trial will reduce loss to follow-up for longitudinal assessments by engaging the dyads every 6 months throughout the study (6, 12, 18, and 24 months). This includes keeping the assignment of research staff and participants consistent at each outcome assessment, sending reminder letters before each assessment, and sending birthday cards signed by the study team. This strategy has produced a <1% loss to follow-up in the pilot study.

Statistical Plan

Overview

Our study is a three-arm RCT to determine the impact of AD screening on older adults' family members. By design, it will also test the congruence of outcomes between the patient and family member. The 1:1:1 randomization creates three randomized groups.

- For analysis, we will first examine univariate distributions of continuous variables in order to detect any potential violations of assumptions to our planned parametric methods of analyses.
- Variables will be transformed as needed to ensure normal distribution assumptions are met.
- We will use nonparametric methods if transformations are inadequate.
- Demographic characteristics will be compared among the groups in order to evaluate whether the randomization effectively balance the dyads.
- We will use Chi-squared tests or Fisher's exact tests to compare the frequencies of categorical variables. Analysis of variance (ANOVA) or its nonparametric alternative, the Wilcoxon rank sum test, will be used to compare the distribution of continuous variables among the groups.
- All analyses will be conducted using SAS 9.4 (SAS Institute, Carey, North Carolina).

Primary Aim

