- **Multi-level mixed effects models** will be used to examine differences in SF-36 scores for both patients and family members using dyadic analytic approaches. For this aim, we will compare family members in the two screening groups (Screen Only and Screen Plus) to those in the no screening (Control) group. Repeated SF-36 scores from both patients and family members will be included as the outcome variables with participant type (patient or family member), group (Screening Only and Screening Plus versus Control), time, and interaction between groups and time as independent variables. We will use a multi-level variance-covariance matrix in the mixed effects models to account for two sources of potential correlations. Correlations from measures obtained from the same individual over time, an autoregressive correlation will be used. Correlations within a dyad between a patient and his/her family member. A compound symmetry structure will be used for the within-dyad correlation. Parameter estimation and hypothesis tests for the mixed-effects models will be conducted using the maximum likelihood approach that provides robust estimation under the missing at random mechanisms.
- A significant interaction between group and time would indicate differences in changes of SF-36 over time between the two screening groups compared to the no screening group. Absence of significant interactions, significant main group effects will suggest differences in SF-36 between groups' at all follow-up times. For Hypothesis 1 we will use a linear contrast for SF-36 from family members in the combined screening groups (Screen Only and Screen Plus) versus the no screening (Control) group at 24 months. We will also include additional covariates in the mixed effects models to determine whether family member characteristics (relationship to patient, frequency or types of contact, etc.) and knowledge of screening are associated with the outcome measures.

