- **Mixed effects models with Caregiver Preparedness Scale or the Revised Scale for Caregiver Self-Efficacy scores** collected at baseline, 6, 12, 18 and 24 months will be used as the outcome variables, group (Screen Only and Screen Plus versus Control), time and interaction between group and time as independent variables. Linear contrasts will be used to compare preparedness and caregiver self-efficacy scores in the combined screening groups versus the no screening group at 24 months. We will also evaluate potential interactions between patient's/family member characteristics and variables associated with increased level of caregiver preparedness and self-efficacy over time.

Secondary Aim

- **To measure the impact and compare strategies for evaluation and treatment post screening, we will compare quality of life measures, caregiver preparedness, caregiving self-efficacy, depression and anxiety symptoms from family members** in the Screen Only (notify dyad and PCP of results only) group to the Screen Plus (notify dyad and PCP and a referral to ABC Program if screen positive) group using multi-level mixed effects models, similarly to the approach described in details for Aim 1. Separate mixed effects models with SF-36, Caregiver Preparedness Scale, Revised Scale for Caregiver Self-Efficacy, PHQ-9 or GAD-7 scores collected at baseline, 6, 12, 18, and 24 months from family members will be used as the outcome variables. Screening group (Screening Only versus Screening Plus), time and interaction between group and time will be used as independent variables. Linear contrasts will be used to compare all scale scores between the two screening groups at 24 months.

Sensitivity analyses for the impact of refusals and other sources of missing data

- We will compare patient and family member characteristics between those who complete at least one or more follow-up assessment(s) after baseline and those who did not complete any assessment beyond baseline due to refusal or other reasons. Significant variables detected from these comparisons will be included in the mixed effects models for the primary and secondary outcomes as covariates to control for potential bias from those missing follow-up outcomes. Under the missing at random

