assumption, results from the mixed effects models will remain unbiased if the variables contributing to the missing data are included as covariates in the models. We will also perform additional sensitivity analyses to examine whether the missing at random assumption using the selection model approach under an informative missing mechanism impacts our analyses.

Statistical Power

Sample Size and Power Considerations for COADS

For the models in Aims 1, 2 and 3, we assume a base correlation of 0.2 and a decay rate of 0.8 in a linear exponent autoregressive correlation structure for repeated measures and a continuous time response, we will need to have 540 dyads per group to have complete data at 24 month in order to achieve 82.6% power to detect a group by time interaction with an effect size of 0.24 SD with higher SF-36, lower PHQ-9, GAD-7, higher caregiver preparedness and self-efficacy scores at 24 months in the combined screening groups (Screen Only and Screen Plus) compared to family members in the no screening (Control) group. Our previous screening studies and studies in primary care had a 5% loss to follow-up (death or withdraw) within a 12-month period. Therefore, allowing a loss to follow-up rate of 10% over the 24 months, we plan to enroll 600 dyads per group into this study. For Aim 4, using similar assumptions on the correlation structure for repeated measures and also 10% attrition rate, we will have 83.4% power to detect a significant group and time interaction with an effect size of 0.28 SD comparing family members randomized to the screening plus group to those in the screening only group at 24 months. Power estimation was conducted using the GLM Power procedure in SAS.

Timeline

Table 3. Study Timeline	Year 1	Year 2	Year 3	Year 4	Year 5
Hire/ train staff					
Revise protocol manual and database					
IRB modification and approval					
Subject recruitment and consent					
Data collection					
Data analysis					
Prepare abstracts and manuscripts					
Disseminate results

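### On a plain reading, the primary model's covariates are not fixed before follow-up data are seen: some come from a significance screen on missingness, others from an open-ended list

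*Combined protocol and SAP*

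**What the plan says.** Three parts of the Statistical Plan bear on the covariates.

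- **Primary Aim.** The SF-36 model has participant type, group, time and group by time, with a linear contrast of the combined screening groups against control at 24 months. It continues: "We will also include additional covariates in the mixed effects models to determine whether family member characteristics" (relationship to the patient, frequency or types of contact, and so on) and knowledge of screening are associated with outcome. There is no significance condition, and the list is left open.
- **Sensitivity analyses for the impact of refusals and other sources of missing data.** Characteristics are compared "between those who complete at least one or more follow-up assessment(s) after baseline and those who did not complete any assessment beyond baseline". Then: "Significant variables detected from these comparisons will be included in the mixed effects models for the primary and secondary outcomes as covariates". No candidate list, significance level or limit on the number of variables is given.
- **Same section, rationale.** Under missing at random, "results from the mixed effects models will remain unbiased if the variables contributing to the missing data are included as covariates in the models". A further analysis is planned "using the selection model approach under an informative missing mechanism".

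Step 2 (Enrollment) stratifies randomization by site. None of the model descriptions names site as a term.

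**The concern.** A primary model should be determined before anyone sees follow-up data. Here two analysts could follow the text faithfully and fit different primary models. They could choose different candidates, different significance levels and different ends to the open list.

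The screen is also weakly matched to its stated purpose. The rationale requires the variables that drive missingness to be in the model, but a significance test admits them only when it has the power to find them. It selects on association with missingness alone, whereas adjustment removes dropout bias only for variables related to both missingness and outcome. And it classes anyone with a single 6-month visit as followed up, so it says nothing about who leaves between then and 24 months.

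Knowledge of screening raises a separate problem. Table 2 collects it at 6, 12, 18 and 24 months, and it is a direct consequence of allocation. Including it in the primary model could absorb part of the effect being estimated.

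**Working it through.** **1. The plan's own figures.** Statistical Power states that "we will need to have 540 dyads per group to have complete data at 24 month in order to achieve 82.6% power" for 0.24 SD.

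- Inputs from the plan: five visits; linear exponent autoregressive correlation with base 0.2 and decay 0.8; 1:1:1 allocation, hence 1,080 against 540.
- Assumptions: alpha 0.05; group difference rising linearly from 0 to the stated effect.
- Correlation at lag k is 0.2^(1 + 0.8(k−1)/3), giving 0.200, 0.130, 0.085 and 0.055.
- Multivariate group-by-time F test with 4 and 1,615 df, noncentrality 12.71: power **82.6%**.
- Aim 4 (540 against 540, 0.28 SD), noncentrality 12.97: **83.4%**.
- Enrolment: 540/0.9 = **600** per group.

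All three reproduce, and the covariate rule changes none of them.

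**2. Power of the screen.** The documents do not say how many will have no follow-up. Spreading the 5% 12-month loss evenly gives 1,800 × (1 − 0.95^0.5) = 45.6, or about 46 lost before 6 months (assumption).

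SE of the standardized difference = √(1/46 + 1/1,754) = 0.149. Probability of selection = Φ(d/SE − 1.96):

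- d = 0.30: Φ(2.009 − 1.96) = **52%**
- d = 0.25: Φ(1.674 − 1.96) = **39%**

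Range over the assumed share with no follow-up:

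| No follow-up | 0.2 SD | 0.3 SD | Binary trait, 40% vs 30% |
|---|---|---|---|
| 1% (18) | 13% | 24% | 17% |
| 2.5% (45) | 26% | 51% | 31% |
| 5% (90) | 46% | 79% | 52% |
| 10% (180) | 72% | 97% | 77% |

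The plan's 10% is total loss over 24 months, so the group with no follow-up at all should be smaller and the upper rows are the more relevant ones.

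**3. Chance selections.** With k unrelated, independent candidates tested at 5%, P(at least one enters) = 1 − 0.95^k: 23% for 5, 40% for 10, 64% for 20 (k is assumed).

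**4. What a missed predictor does to the estimate.** The covariate mean among those remaining moves by (fraction lost) × d. Multiply by the covariate's effect on outcome, assumed 0.3 SD per SD.

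- 46 lost across all arms: 46/1,800 × 0.3 × 0.3 = 0.002 SD in each arm, which cancels between arms.
- All 46 in the control arm: 46/600 × 0.3 × 0.3 = **0.007 SD**, about 3% of 0.24 SD.
- 10% loss by 24 months, selective only in the control arm: 0.10 × 0.3 × 0.3 = **0.009 SD**, about 4% of 0.24 SD.

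**5. Simulation** (2,500 replicates; 24-month ANCOVA, 1,200 against 600). Assumptions: ten baseline covariates; three prognostic at 0.3 SD each; one of these drives dropout at log-odds 0.2 per SD; 2.5% to 10% missing.

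- Type I error: 4.3–5.4% with screen-selected covariates, 4.6–5.5% with all ten fixed.
- Largest bias, when the predictor acted only in the screened arms at 10% loss: about 0.005 SD with the screen, 0.008 SD with no covariates.
- At 10% loss, SE was 0.053 (none), 0.051 (screen) and 0.045 (fixed). Power for 0.15 SD was 80%, 83% and 90%.

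Two limits apply. The simulation used one dropout indicator for both the screen and the 24-month outcome, which favours the screen. And three covariates at 0.3 SD explain 3 × 0.09 = 27% of variance. If stable covariates with constant effects explained that much at every visit, and residual correlations were not negative, repeated scores would correlate at 0.27 or more. The plan assumes 0.055 between baseline and 24 months. At 5.5% explained, the SE falls only by 1 − √0.945 = 3%, against 1 − √0.73 = 15% at 27%. The precision gain is therefore a range.

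**The case against.** The rule is written in advance, and it screens characteristics against non-return rather than against outcome scores or the treatment effect. It is not a search for a favourable estimate, and calling it post hoc would be wrong. Only its result depends on the data.

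Nor do covariates enter solely by passing the screen: the Primary Aim section adds relationship and contact variables with no significance condition. That stands, but it does not fix the model, because the list is open, its stated purpose is to study associations, and it includes a post-randomization variable.

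The heading says sensitivity analyses, and the next step is described as additional sensitivity work, so the authors may have meant only a sensitivity version. This is a fair reading. The sentence itself, however, refers to the models for the primary and secondary outcomes, and nowhere does the plan say that an unadjusted model remains primary. The ambiguity itself needs resolving.

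Finally, likelihood estimation already uses the observed repeated scores under missing at random, and the selection model addresses informative missingness. Both limit the damage. The pilot's loss of under 1% cuts both ways: fewer losses weaken the screen but also shrink any bias.

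**Conclusion.** The point holds as one of model specification. On a plain reading, the primary covariate set is open by two routes until follow-up data are seen. The screen would also miss a true 0.3 SD predictor of non-return about half the time, and it does not look at dropout after the first follow-up. This rests on an assumed 46 dyads without follow-up and an assumed two-sided 5% level.

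A reader might infer that the rule materially biases the treatment comparison or inflates type I error. The figures do not support that: bias stays below 0.01 SD in every case examined, and simulated type I error stays near 5%. A low probability of selecting a covariate is not bias in the treatment effect, and an irrelevant baseline covariate among 1,800 randomized dyads does essentially no harm.

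The real costs are a primary model that is not pinned down and some precision forgone. The precision gain runs from about 3% of the SE under the plan's own correlation assumption to about 15% under strong prognostic covariates, both relative to no adjustment. The stated power and sample size are unaffected.

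**What to change.** 1. In the Primary Aim section, define the primary model with a fixed covariate set: site, as the stratification factor, plus a short named list of baseline variables already collected under Table 2. Relationship to the patient, frequency of contact, education level and self-reported health status are examples. Carry the same set into the secondary-outcome models.
2. Exclude knowledge of screening from the primary model. Any analysis of its association with outcome should be separate and labelled exploratory.
3. State that covariates selected for their association with missingness are used only in a labelled sensitivity analysis. Give the candidate list and significance level there, and base the comparison on a missing 24-month outcome rather than on having no follow-up at all. Say whether the patient's or the family member's missingness defines it.

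The cost is SAP wording, a few more fixed-effect parameters and no later choice of covariates. No new data and no change in sample size are needed.
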